3.6. Determination of Sample Size

Sample size was determined based on a two-sided comparison between RTB101 and placebo. In parts 1 and 2 of the Phase 2b trial, 28.2% of subjects had a clinically symptomatic respiratory illness on placebo (excluding subjects with COPD and current smokers). With an assumed Week 16 clinically symptomatic respiratory illness incidence of 28.2% on placebo and 19.7% in the RTB101 arm, a total sample size of approximately 1066 subjects (equally randomized) will provide 90% power to detect a 30% reduction in the percentage of subjects with clinically symptomatic respiratory illness between RTB101 and placebo using a two-sided test of 0.05 significance. Power analysis was conducted using Likelihood Ratio Chi-square Test.

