9.2.2. Secondary Objective Estimands

1. The estimand for the secondary objective “To determine if RTB101 as compared to placebo decreases the percentage of subjects with a CSRI associated with ≥ 1 laboratory-confirmed pathogen(s) through Week 16” is defined by the following:

- Population:
 - Subjects in FAS population
- Variable:
 - Occurrence of a CSRI with ≥ 1 laboratory-confirmed pathogen(s) by the Week 16 visit

This document is confidential.

- Intercurrent events:
 - If a subject discontinues study prematurely due to an RTI AE or RTI SAE and the subject did not meet the definition of a CSRI associated with ≥ 1 laboratory-confirmed pathogen(s), assume the subject experienced a CSRI with ≥ 1 laboratory-confirmed pathogen(s)
 - If a subject discontinues study prematurely for any reason other than an RTI AE or RTI SAE, and the subject did not meet the definition of a CSRI associated with ≥ 1 laboratory-confirmed pathogen(s), impute the subject did not have a CSRI with ≥ 1 laboratory-confirmed pathogen(s)
 - If a subject completed the study and has intermittent missing eDiary data and the subject did not meet the definition of a CSRI associated with ≥ 1 laboratory-confirmed pathogen(s), impute the subject did not have a CSRI with ≥ 1 laboratory-confirmed pathogen(s)
 - Population-level summary:
 - odds ratio, i.e. the ratio of the odds of having a CSRI with ≥ 1 laboratory-confirmed pathogen(s) in subjects treated with RTB101 compared to the odds of having a CSRI with ≥ 1 laboratory-confirmed pathogen(s) in subjects treated with placebo by the Week 16 visit
2. The estimand for the secondary objective “To determine if RTB101 as compared to placebo decreases the rate of CSRIs, with or without an associated laboratory-confirmed pathogen, through Week 16” is defined by the following:
- Population:
 - Subjects in FAS population
 - Variable:
 - Number of CSRIs with or without an associated laboratory-confirmed pathogen through the Week 16 visit
 - Intercurrent events:
 - If a subject discontinues study prematurely due to an RTI AE or RTI SAE and the subject did not meet the definition of a CSRI, assume the subject experienced one CSRI
 - If a subject discontinues study prematurely for any reason other than an RTI AE or RTI SAE and the subject did not meet the definition of a CSRI, impute the subject did not have a CSRI

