9.4. Analyses of Secondary Efficacy Endpoints

9.4.1. Percentage of Subjects with One or More Clinically Symptomatic Respiratory Illnesses Associated with ≥ 1 Laboratory-confirmed Pathogen(s)

The percentage of subjects with CSRI associated with ≥ 1 laboratory-confirmed pathogen(s) beginning at least 3 days after the start of study drug treatment through Week 16 (H_2) as assessed by pre-specified clinical diagnostic criteria and respiratory pathogen PCR of nasopharyngeal swabs, sputum gram stain and culture, and/or RIDTs will be analyzed in the same manner as the primary efficacy analysis as described in 9.3.1 based on the estimand for the secondary objective corresponding to this endpoint described in 9.2.2 above.

Laboratory results from a specimen obtained within 3 days before the CSRI start date through the CSRI end date will be used to determine if the CSRI is associated with ≥ 1 laboratory-confirmed pathogen. Laboratory confirmation includes a positive respiratory pathogen PCR of nasopharyngeal swabs, sputum gram stain and culture, and/or RIDT. If multiple specimens are obtained for a particular CSRI, then any positive result will be counted as laboratory confirmation if it occurs within 3 days before the CSRI start date through the CSRI end date. A laboratory-confirmed CSRI may be associated with multiple pathogens. Note that organisms considered to identify a positive sputum specimen should meet standard microbiological laboratory criteria of growing from a sputum specimen with > 25 WBC/hpf and < 10 Squamous cells/ hpf, and they have matching morphology on gram stain and culture.

Summary statistics will be presented along with a full data listing by treatment group.

9.4.2. Rate of Clinically Symptomatic Respiratory Illnesses (with or without an Associated Laboratory-confirmed Pathogen)

The rate of CSRI (with or without an associated laboratory-confirmed pathogen) beginning at least 3 days after the start of study drug treatment through Week 16 (H_3) will be analyzed based on the negative binomial distribution. The first 3 days of study drug treatment will not be included in determining the denominator of rate.

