A generalized linear model analysis will be conducted using the number of CSRI per 16-week period (illnesses/16 weeks) as the dependent variable and will include treatment group, age (continuous covariate), Clinical Frailty Scale score (ordinal covariate), medical history of diabetes mellitus type 2 (Y/N), medical history of asthma (Y/N) medical history of CHF (Y/N), and receipt of current season influenza vaccination (Y/N) as fixed effects.

This document is confidential.

The rate ratio (RR) (RTB101 dose group to placebo) of the treatment effect will be derived from the model along with the 95% 2-sided confidence interval (CI). Model-adjusted mean rates for each treatment group and their corresponding 95% 2-sided CI will also be calculated.

The “log” link function will be used in the model and an offset term will be included to account for variable lengths of treatment exposure across the subjects. The unadjusted rate of CSRI per subject through Week 16 will be calculated by summing the number of total CSRIs per subject through Week 16 within each treatment group.

Analysis of this endpoint will be based on the estimand for the secondary objective corresponding to this endpoint described in 9.2.2 above.

Summary statistics will be presented along with a full data listing by treatment group.

9.4.3. Rate of Clinically Symptomatic Respiratory Illness Associated with ≥ 1 Laboratory-confirmed Pathogen(s)

The rate of CSRIs associated with ≥ 1 laboratory-confirmed pathogen(s) beginning at least 3 days after the start of study drug treatment through Week 16 (**H₄**) as assessed by pre-specified clinical diagnostic criteria and respiratory pathogen PCR of nasopharyngeal swabs, sputum gram stain and culture, and/or RIDTs will be analyzed in the same manner as described in 9.4.2 above, based on the estimand for the secondary objective corresponding to this endpoint described in 9.2.2 above. Section 9.4.1 describes which laboratory result will be used to determine if the CSRI is associated with ≥ 1 laboratory-confirmed pathogen.

Summary statistics will be presented along with a full data listing by treatment group.

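### SAP 9.4.2 describes the rate response as already scaled to 16 weeks and adds a time offset, while the H3/H4 estimands define a count; the unadjusted rate has no divisor, and the exit rule can drop a few events

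*SAP*

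**What the plan says.** SAP 9.4.2 analyses H3 with a negative binomial model and a log link. It fits this model "using the number of CSRI per 16-week period (illnesses/16 weeks) as the dependent variable", and adds that "an offset term will be included to account for variable lengths of treatment exposure across the subjects". The section also says "The first 3 days of study drug treatment will not be included in determining the denominator of rate", without defining that denominator further. For the descriptive summary it says "The unadjusted rate of CSRI per subject through Week 16 will be calculated by summing the number of total CSRIs per subject", within each treatment group, and names nothing to divide by.

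The same section ties the analysis to the estimand in SAP 9.2.2. There, item 2 (H3) and item 3 (H4) define the variable as a number of CSRIs. If a subject leaves the study because of an RTI adverse event or serious adverse event "and the subject did not meet the definition of a CSRI, assume the subject experienced one CSRI". Item 3 has the parallel rule for laboratory-confirmed CSRIs.

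SAP 9.4.3, 9.5.2 and 9.5.25 send H4, H7 and H8 to the 9.4.2 method, as do the other rate endpoints in 9.5. H3, H4, H7 and H8 all belong to the alpha-controlled sequence in SAP 9.1.

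**The concern.** A negative binomial model with a log-time offset takes the raw count as its response, and the offset converts the fitted mean into a rate. If the count has first been divided by time, short follow-up is corrected twice. Subjects who leave early then carry inflated responses, with more variance than the model allows for, so standard errors come out too small. If exits differ between arms, the rate ratio also shifts. The choice between the two codings should not be left to the programmer in a confirmatory test.

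The offset has a problem of its own. It is tied to treatment exposure, and the only exposure definition in the SAP (10.1) removes drug interruptions. Protocol 5.5.2 keeps subjects in follow-up, with daily eDiary entries, after drug is stopped. CSRIs in that period are counted, but their time at risk would not be.

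The remaining two issues are lesser. A sum is not a rate per subject. The exit rule was carried over from the yes/no primary endpoint, where one event per subject is enough; in a count it can omit a later illness.

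**Working it through.** **1. The plan's own figure.** SAP 3.6 assumes "incidence of 28.2% on placebo and 19.7% in the RTB101 arm", "using a two-sided test of 0.05 significance", and says that "a total sample size of approximately 1066 subjects (equally randomized) will provide 90% power to detect a 30% reduction". The likelihood-ratio chi-square test with 533 per arm gives power 0.903, and 528 per arm suffices for 90%. The figure reproduces. It concerns the primary endpoint and is not affected by this point. The documents give no event count or power for the rate endpoints.

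**2. Rates for illustration (assumed).** Converting incidence by rate = -ln(1 - p): placebo -ln(0.718) = 0.331 and RTB101 -ln(0.803) = 0.219 per 16 weeks, ratio 0.662. Expected events with full follow-up: 533 x 0.3313 + 533 x 0.2194 = 176.6 + 116.9, about 294. Time at risk: 112 - 3 = 109 days.

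**3. One subject with one CSRI.** Let t be the observed fraction of 109 days. Count plus offset implies 1/t per 16 weeks; scaled response plus offset implies 1/t².

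| Days observed | Count + offset | Scaled + offset |
|---|---|---|
| 28 | 3.9 | 15.2 |
| 56 | 1.9 | 3.8 |
| 109 | 1.0 | 1.0 |

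Only subjects with incomplete follow-up are affected.

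**4. Simulation of the test.** 533 per arm, rates from step 2, dispersion 0.5 treated as known, dropout times uniform, no covariates, 1000 runs under no effect. Dispersion and dropout pattern are assumptions. The 5.1% is the Phase 2b missing-data rate in protocol 9.4.2, used as a proxy for dropout.

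| Dropout, placebo/RTB101 | Type I error, count + offset | Type I error, scaled + offset | Null rate ratio, scaled + offset |
|---|---|---|---|
| 0/0 | 5.4% | 5.4% | 0.998 |
| 5.1%/5.1% | 5.7% | 7.5% | 1.004 |
| 10%/10% | 5.2% | 9.9% | 1.000 |
| 5%/10% | 4.2% | 8.6% | 1.022 |
| 5%/15% | 4.2% | 11.4% | 1.055 |

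Simulation error near 5% is sqrt(0.05 x 0.95/1000) = 0.7 points. A repeat with dispersion estimated (400-800 runs per scenario) gave 6.8% against 5.4% at 5.1% dropout in both arms, and 7.8% against 4.4% at 10% in both.

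**5. Shift in the ratio.** With a fraction d leaving at uniform times, mean follow-up is 1 - d/2. Double scaling gives approximately rate/(1 - d/2). For assumed exits of 4% on placebo and 8% on RTB101 the ratio is multiplied by 0.98/0.96 = 1.021, towards less benefit. Reversed exits give 0.96/0.98 = 0.980, towards more. Balanced exits give no shift.

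**6. Unadjusted rate.** At 5.1% dropout in both arms, the sums as written would be about 172 and 114. Divided by time at risk they become about 0.33 and 0.22 per 16 weeks. With the 4%/8% exits, the ratio of sums is off by 0.96/0.98 = 0.980.

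**7. Exit rule.** Exits: 1066 x 0.051 = 54.4. If 5-20% of these are due to an RTI (assumed), 2.7 to 10.9 subjects are concerned. If 28.2% of them had an earlier CSRI (the placebo incidence, an assumed upper value), 0.8 to 3.1 events are lost, or 0.3-1.0% of 294. A stress case of 10% exits, half due to RTI, gives 1066 x 0.10 x 0.5 x 0.282 = 15 events (5%).

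**The case against.** The best defence is that the response was always meant to be a count. The primary analysis period is 16 weeks for every subject, so the bracketed unit can be a label. The estimands say number of CSRIs, SAP 9.4.2 and protocol 9.5 specify a negative binomial model, and a log link with an offset is the usual set-up for a count. This stands: a reader might infer that the SAP prescribes a double correction, but the documents support only that its wording permits one.

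The unadjusted figure enters no test, since the rate ratio and its interval come from the model. The omitted divisor is an incomplete sentence; the plan never says to leave it out. This also stands.

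On the exit rule, a reader might infer that the most serious RTIs are left out, for example a pneumonia that ends follow-up in week 10 after a CSRI in week 3. The documents do not support that. Protocol 6.7.1 lists pneumonia among the illnesses a CSRI may include. Under SAP 7.2.1 a later episode that meets the eDiary definition after at least 7 symptom-free days counts as a second event. Only an exit RTI that fails the definition goes uncounted. The rule is explicit and identical in both arms, so the choice is defensible as an estimand, though it fits poorly with a count of repeated illnesses. It is written only for the CSRI estimands and does not reach H7 or H8.

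The 8%/4% split is not in the documents, and with balanced exits both 2% shifts vanish. A claim that model-based and unadjusted rates err in opposite directions would need both literal readings and unequal exits together.

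**Conclusion.** SAP 9.4.2 and SAP 9.2.2 give two descriptions of the response for the same confirmatory test, and only one is valid with the stated offset. Coded literally, the type I error rises modestly, to about 7-8% against 5% at about 5% dropout in both arms, and the rate ratio moves by about 2% if exits are 8% and 4%. These figures rest on an assumed dispersion of 0.5 and uniform dropout times; more or less even dropout makes them larger. The treatment-exposure offset is a separate mismatch that correcting the response alone would leave in place. Its size cannot be worked out from the documents.

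The missing divisor affects presentation only. The exit rule costs about 1-3 events of roughly 294 under assumed exit rates. To say that the rate endpoints miscount events in general would go too far: only the exit rule concerns counting, and the other faults concern scaling. The primary endpoint and the sample size are untouched. The changes should be made before unblinding, because the affected tests are alpha-controlled and the correction is cheap.

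**What to change.** In SAP 9.4.2:

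- State that the response is the integer number of CSRIs, and that time enters only through the offset.
- Replace treatment exposure with time under observation: offset = log of days observed after the first 3, that is from Day 4, up to the cut-off in SAP 7.2.1 or earlier exit. For H7 and H8, which are not diary endpoints, say that this means time in study.
- Define the unadjusted rate as total CSRIs divided by the same total observation time, expressed per 16 weeks, by arm.

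As a secondary change, in SAP 9.2.2 items 2 and 3, count an exit RTI that did not itself meet the definition as one further event regardless of earlier CSRIs. If the present rule is kept on purpose, say so.

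The cost is a few sentences in the SAP and matching programming specifications. No new data are needed.

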9.4.4. Time to Alleviation of Moderate and Severe Respiratory Illness Symptoms

The time to alleviation of moderate and severe symptoms due to a CSRI beginning at least 3 days after the start of study drug treatment through Week 16 (**H₅**) will be analyzed as a secondary endpoint.

The time to alleviation of moderate or severe symptoms is defined as the time when all of 6 respiratory symptoms (runny nose, sneezing, stuffy nose, sore throat, hoarseness, or cough) and 3 general symptoms (headache, feverishness/chills or loss of appetite) have been assessed by the patient as Absent or Mild in the patient eDiary from the earliest start date of any moderate or severe symptoms associated with the CSRI among all subjects with ≥ 1 CSRI through the Week 16 visit. For subjects with >1 CSRI, the longest time to alleviation of moderate or severe symptoms among the CSRIs will be used for the analysis.

The time to alleviation of moderate and severe symptoms (days) = (earliest date all symptoms due to a CSRI are Absent or Mild – earliest start date among all moderate or severe symptoms) +1

Risk set: Subjects who have a ≥ 1 CSRI.

Time origin: Earliest start date of moderate or severe symptom associated with a CSRI.

For subjects who were not observed to have an alleviation of their moderate or severe symptoms, time to alleviation of moderate or severe symptoms will be censored on the date of last eDiary entry.

This document is confidential.

The point estimate of the hazard ratios and the associated 95% confidence intervals for RTB101 versus placebo will be obtained using the Cox proportional hazards regression model with fixed effects for treatment group, age (continuous covariate), Clinical Frailty Scale score (ordinal covariate), medical history of diabetes mellitus type 2 (Y/N), medical history of asthma (Y/N) and medical history of CHF (Y/N) as covariates. An approximate Chi-square test based on Wald statistic will be used to compare treatment groups.

Summary statistics and associated survival curves (Kaplan-Meier estimates) will be presented along with a full data listing by treatment group.

9.4.5. Percentage of Subjects with Severe Symptoms due to Clinically Symptomatic Respiratory Illnesses

The percentage of subjects with severe symptoms due to CSRIs beginning at least 3 days after the start of study drug treatment through Week 16 (H_6) will be analyzed in the same manner as the primary efficacy endpoint, as described in [9.3.1 above](#) based on the estimand for the secondary objective corresponding to this secondary endpoint as described in [9.2.2 above](#).

Summary statistics will be presented along with a full data listing by treatment group.

9.4.6. Rate of Clinically Symptomatic Respiratory Illnesses Associated with Specific Laboratory-confirmed Viruses

A comparison of the rate of clinically symptomatic respiratory illnesses associated with specific laboratory-confirmed viruses (coronaviruses, hMPV, HRV/enterovirus, adenovirus, influenza A and B virus, parainfluenza viruses, and RSV) beginning at least 3 days after the start of study drug treatment through Week 16 as assessed by respiratory pathogen PCR of nasopharyngeal swabs and/or RIDTs is not powered to demonstrate a pre-specified treatment effect. This endpoint will be analyzed in the same manner as described in [9.4.2 above](#). However, there will be no formal statistical tests conducted and no p-values will be presented. To demonstrate trends consistent with the primary endpoint for the pre-specified laboratory-confirmed viruses, the estimated rate of the laboratory-confirmed viruses and associated CIs will be presented by treatment arm.

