because some infectious pathogens may not be detected with the proposed laboratory detection methods. Data from Phase 2 studies suggest that RTB101 upregulates antiviral defenses and decreases the incidence of respiratory illness associated with multiple different viruses. Clinically symptomatic respiratory illnesses beginning at least 3 days after the start of study drug treatment will be analyzed because RTIs may have a 3-day incubation period. Therefore, RTIs occurring during the first 3 days of the study may have been acquired prior to initiation of study drug treatment. The clinical criteria that will be used in the Phase 3 trial to diagnose clinically symptomatic respiratory illnesses (see Section 6.7.1) capture RTI events that were also captured in the Phase 2b (RTB-BEZ235-202) trial. Prespecified clinical criteria will be used to diagnose clinically symptomatic respiratory illnesses to make sure that diagnosis is consistent across sites.

Secondary Endpoints

Secondary endpoints will include the incidence of clinically symptomatic respiratory illnesses associated with laboratory-confirmed pathogen(s). Assessment of clinically symptomatic respiratory illness that is associated with an infectious pathogen will allow assessment of the treatment effect of RTB101 on respiratory illness that is confirmed to be infectious in etiology. The incidence of clinically symptomatic respiratory illnesses associated with specific viruses (e.g., coronaviruses, hMPV, HRV/enterovirus, adenovirus, influenza A and B virus, parainfluenza viruses, and RSV) will also be assessed as a secondary endpoint to determine if RTB101 has consistent benefit across different viral infections, and to demonstrate no enhancement of any viral infection. Another secondary endpoint will be rate of clinically symptomatic respiratory illness because subjects may experience more than one respiratory illness during the 16-week treatment period, and RTB101 may decrease not just the percentage of subjects with clinically symptomatic respiratory illness but also the rate of clinically symptomatic respiratory illnesses. Additional secondary endpoints will determine if RTB101 decreases not only the incidence but also the severity and duration of respiratory illness symptoms. Decreasing the severity and duration of respiratory illness symptoms is a clinically important endpoint and will provide further evidence of the clinical benefit of RTB101.

Exploratory Endpoints

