9.4.1. Statistical Model, Hypothesis, and Method Analysis

This is a Phase 3, multi-center, randomized, double-blind, placebo-controlled, parallel-group study to evaluate the efficacy and safety of RTB101 10 mg to prevent clinically symptomatic respiratory illness in the elderly. All eligible subjects will be randomized in a 1:1 ratio at Baseline to receive either RTB101 10 mg or placebo.

The statistical model for the binary endpoint is logistic regression model.

Null hypothesis: The true underlying percentage of subjects with at least 1 clinically symptomatic respiratory illness (with or without an associated laboratory-confirmed pathogen) by Week 16 is equal between RTB101 10 mg and placebo.

Alternate hypothesis: The true underlying percentage of subjects with at least 1 clinically symptomatic respiratory illness (with or without an associated laboratory-confirmed pathogen) is not equal between RTB101 10 mg and placebo.

The primary efficacy endpoint will be analyzed through a logistic regression model to obtain an estimate of the population odds ratio and associated CIs between RTB101 and placebo. This primary efficacy model will be adjusted for factors that may influence response to treatment for

clinically symptomatic respiratory illness, such as age, frailty score, receipt of current season influenza vaccination and medical history of asthma, CHF, or Type 2 diabetes mellitus.

In testing multiple hypotheses, control of the study-wise error rate will be implemented. As the number of statistical tests within a trial increases (multiplicity), the chance of making a false conclusion (false positive) about a drug's effect with respect to at least one of the endpoints increases, if multiplicity is not addressed. In this study, a fixed sequence gate-keeping strategy will be used to control the study-wise error rate at a 2-sided α -level of 0.05. The following primary, secondary and exploratory efficacy endpoints will be tested in the sequence specified below:

Order	
H ₁	The percentage of subjects with 1 or more CSRI (with or without an associated laboratory-confirmed pathogen) beginning at least 3 days after the start of study drug treatment through Week 16.

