Next, we demonstrate the evaluation of the secondary endpoint of time to alleviation of moderate and/or severe clinically symptomatic respiratory illness symptoms through Week 16. The point estimate of the hazard ratios and the associated 95% CIs for RTB101 versus placebo will be obtained using the Cox proportional hazards regression model with fixed effects for treatment group and covariates consistent with the primary endpoint. An approximate Chi-square test based on Wald statistic will be used to compare treatment groups. Survival curves (Kaplan-Meier estimates) for the “time to alleviation” (i.e., proportion with no alleviation) may be presented by treatment group.

Exploratory efficacy endpoints will be evaluated in a similar fashion as the primary or secondary endpoints, the same set of covariates as for the primary analysis model will be included in each model. Specifically, exploratory endpoints with a binary outcome will be analyzed using the same methods as the primary endpoint. Time-to-event exploratory endpoints will be evaluated using the Cox proportional hazard model, continuous exploratory endpoints may be analyzed using an Analysis of Covariance (ANCOVA) model, or by a mixed model repeated measures model (MMRM).

Exploratory endpoints will be summarized descriptively, as appropriate, continuous endpoints will be summarized with the use of box plots, while proportions will be displayed by histograms. In addition, changes in biomarker levels over time will be described by treatment group. The details of these analyses will be included in the SAP.

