9.3. Primary Efficacy Endpoint Analysis

9.3.1. Primary Analysis of the Primary Endpoint

The primary efficacy endpoint is the percentage of subjects with at least one CSRI, with or without an associated laboratory-confirmed pathogen, beginning at least 3 days after the start of study drug treatment through Week 16 (H₁).

The primary efficacy endpoint will be analyzed through a logistic regression model to obtain an estimate of the population odds ratio, i.e. the odds of having a CSRI in subjects treated with RTB101 compared to the odds of having a CSRI in subjects treated with placebo and its associated confidence interval. The logistic regression model will be adjusted for factors that are known to be prognostic of outcome, specifically age (continuous covariate), clinical frailty score (ordinal covariate), medical history of diabetes mellitus type 2 (T2DM, Y/N), congestive heart failure (CHF, Y/N) asthma (Y/N), and receipt of current season influenza vaccination (Y/N). Presence or absence of asthma will be obtained from medical history records and not the stratification level entered at baseline.

Analysis of the primary efficacy endpoint will be based on the estimand for the primary objective described above.

Summary statistics will be presented along with a full data listing

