10.7. Physical Examination

A complete physical examination will be done at Screening, Week 16, and Week 20. A targeted physical exam of at least oral cavity, skin, heart and lungs will be done at all other visits. Listings will be provided for all physical exams.

This document is confidential.

11. Interim Analyses

There is no planned interim analysis.

This document is confidential.

12. Changes from Analysis Planned in Protocol

The following changes from the analyses planned in the protocol were included in this SAP:

- (1) The subgroup analysis by gender was added (see [Section 7.6 above](#)) to the list of subpopulations specified in Section 9.4.4.2 of the protocol.
- (2) In Section 9.4 of the protocol, it was stated that no imputation for missing data will be done for the primary analysis of the primary efficacy endpoint. This was modified such that subjects who discontinued study prematurely due to an RTI AE or RTI SAE will be imputed to have experienced a CSRI (see [Section 7.3 above](#)),
- (3) An additional factor, i.e. receipt of current season influenza vaccination (Y/N), was added (see [Section 9.3.1 above](#)) to the logistic regression model specified for the primary analysis of the primary efficacy endpoint specified in Section 9.4.1 the protocol.
- (4) In Section 9.4.1 of the protocol, a gate-keeping strategy for testing multiple endpoints for a primary family (F_1), secondary family (F_2) and exploratory family (F_3) of endpoints was specified. The testing strategy was modified such that families of endpoints will no longer be defined; instead a set of 9 endpoints will be tested using a fixed sequence gate-keeping strategy, as specified in [Section 9.1 above](#).
- (5) Supplemental analyses for the Completers 1 and Completers 2 populations described in [Section 9.3.2.2 above](#) were added.
- (6) Analyses of 4 endpoints not specified in the protocol were included here (see [Sections 9.5.26, 9.5.27, 9.6.1 and 9.6.2 above](#)) as exploratory and/or sensitivity analyses, specifically the analyses of
 - a. the percentage of subjects with expanded-definition CSRI (with or without an associated laboratory-confirmed pathogen) beginning at least 3 days after the start of study drug treatment by Week 16,
 - b. the rate of expanded-definition CSRI (with or without an associated laboratory-confirmed pathogen) beginning at least 3 days after the start of study drug treatment by Week 16,

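### The SAP's H5 Cox model drops influenza vaccination against the protocol's covariate rule; separately, its longest-episode rule lets the number of repeat CSRIs into a duration test

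*SAP*

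**What the plan says.** **Covariates.** Protocol 9.5 specifies the H5 Cox model "with fixed effects for treatment group and covariates consistent with the primary endpoint". For the primary model, Protocol 9.4.1 names "age, frailty score, receipt of current season influenza vaccination and medical history of asthma, CHF, or Type 2 diabetes mellitus", and SAP 9.3.1 fixes the same six factors. SAP 9.4.4 lists treatment, age and frailty score and then ends with "medical history of diabetes mellitus type 2 (Y/N), medical history of asthma (Y/N) and medical history of CHF (Y/N) as covariates". Vaccination is not in that list. The negative binomial model in SAP 9.4.2 keeps it ("and receipt of current season influenza vaccination (Y/N) as fixed effects"), and so does the length-of-stay model in SAP 9.5.9.

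**Repeat episodes.** SAP 9.4.4 restricts the risk set to subjects with at least one CSRI. For a subject with several, "the longest time to alleviation of moderate or severe symptoms among the CSRIs will be used for the analysis". Protocol 9.5 and estimand 5 in SAP 9.2.2 do not mention this rule. The SAP's index of tables plans one Cox table for H5 and no first-episode or all-episode version.

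**Purpose and gate.** Protocol 3.2 says: "Additional secondary endpoints will determine if RTB101 decreases not only the incidence but also the severity and duration of respiratory illness symptoms". Under SAP 9.1, H5 is tested at two-sided 0.05 only after H1 to H4 are all significant.

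**The concern.** H5 is a confirmatory test, and as written its model is not the one the protocol calls for. Two candidate models for one gated test leave a choice that should be closed before unblinding.

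The longest-episode rule is a matter of interpretation. The longest of two illnesses tends to exceed a single one, so an arm with fewer repeats tends to show shorter times. H5 is reached only after the CSRI rate endpoints (H3, H4) have succeeded, which is when the arms are most likely to differ in repeats. A significant H5 could then be read as shorter illness when part of the signal is fewer illnesses.

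**Working it through.** **1. Covariates, side by side.**
- Protocol 9.4.1 and SAP 9.3.1 (primary): age, frailty, T2DM, CHF, asthma, vaccination.
- SAP 9.4.2 (rates) and 9.5.9 (length of stay): the same six.
- SAP 9.4.4 (H5): age, frailty, T2DM, asthma, CHF.
- SAP Section 12, item 3, on the primary logistic model: "An additional factor, i.e. receipt of current season influenza vaccination (Y/N), was added". No item removes the factor from the Cox model.

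One factor is missing in one place. No arithmetic applies.

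**2. The plan's own figure.** Protocol 9.6 gives 28.2% v 19.7%, 1066 subjects and 90% power. The pooled two-proportion formula gives 528 per arm (1056), and power at 533 per arm is 90.3%. With an exact 30% reduction (0.7 × 28.2% = 19.74%) the likelihood-ratio test gives 1066. The figure reproduces. No power or effect size is stated for H5.

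**3. H5 risk set.** 533 × 0.282 ≈ 150 placebo and 533 × 0.197 ≈ 105 RTB101 subjects.

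**4. Repeat share among ill subjects (Poisson).** Time at risk is 109 days (Day 4 to Day 112). SAP 7.2.1 requires 7 clear days before a new CSRI. Assuming 7 or 14 days ill, each episode blocks a new one for b = 14 or 21 days.
- Rate: μ = −ln(1 − p), so 0.3313 (placebo) and 0.2194 (RTB101).
- With m = μ(109 − b)/109, the repeat share is [1 − e^(−m) − m·e^(−m)]/p.
- b = 14: placebo m = 0.2887, 0.0345/0.282 = 12.2%; RTB101 m = 0.1912, 0.0161/0.197 = 8.2%.
- b = 21: placebo m = 0.2675, 0.0300/0.282 = 10.6%; RTB101 m = 0.1771, 0.0140/0.197 = 7.1%.

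**5. Hand check of the shift.** Take equal, independent durations in both arms and at most two episodes per subject. A placebo subject with i episodes has the longer maximum than an RTB101 subject with j episodes with probability i/(i + j). For b = 14:

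0.878 × 0.918 × 1/2 + 0.122 × 0.918 × 2/3 + 0.878 × 0.082 × 1/3 + 0.122 × 0.082 × 1/2 = 0.4030 + 0.0747 + 0.0240 + 0.0050 = 0.5067.

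The odds, 0.5067/0.4933 = 1.027, approximate the hazard ratio (above 1 means faster alleviation on RTB101). The same sum for b = 21 gives 1.024.

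SE of the log hazard ratio = √(1/150 + 1/105) = 0.127. For HR 1.02, z = 0.0198/0.127 = 0.156, giving favourable rejections of 3.6% and a two-sided total of 5.3%. For HR 1.03, z = 0.232, giving 4.2% and 5.6%.

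**6. Simulation.** 533 per arm, no true effect on duration, two-group Cox Wald test at 1.96, b = 14 or 21. Favourable figures cover within-subject duration correlation 0 to 0.5; two-sided totals are for correlation 0. The gamma frailty variance k is assumed.

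| Counts | Mean HR | Favourable (nominal 2.5%) | Two-sided (nominal 5%) |
|---|---|---|---|
| Poisson | about 1.02 | 3.5-4.2% | 5.1-5.9% |
| k = 1 | 1.03-1.05 | 4.0-5.3% | 6.3-6.7% |
| k = 2 | 1.04-1.07 | about 5-8% | 7.7-8.7% |

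- Among runs with H1 and H3 significant, the favourable figures barely change: 3.6-4.2%, 4.1-5.4% and 5.0-7.6%.
- First CSRI only: 2.2-3.1% favourable across the runs.
- Longest rule, drug with no effect: 2.6-2.8% favourable.
- Longest rule, drug fully protects some subjects and does nothing in the rest, so the repeat share is equal: 2.4-2.5% favourable.

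If the clear-day rule is ignored, k = 2 gives about 11% two-sided. That set-up lets a new CSRI start while the last is still running, which SAP 7.2.1 does not allow.

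Not simulated: covariates, censoring, and the H2 and H4 gates.

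**The case against.** **The covariate looks like a drafting slip, and Protocol 9.4.1 offers its list as examples.** Probably so. But SAP 9.3.1 makes the primary list definite, Protocol 9.5 ties H5 to it, and only H5 departs from it. A reader might infer that the omission biases H5. The documents do not support that: nothing in them gives the association of vaccination with illness duration, or its balance among ill subjects.

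**The worst episode is a prespecified and legitimate target.** This stands. A subject spared a second, longer illness has benefited, and estimand 5 does not say that the target is duration per episode. The extra rejections are false only if H5 is read as Protocol 3.2 presents it, as an effect on duration beyond incidence. That is a reason to state what H5 measures, not to discard the rule.

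**The size rests on assumptions.** This also stands. The documents give no repeat rate, dispersion, illness length or within-subject correlation. Blocks longer than 21 days would make repeats rarer still. The direction needs a drug that lowers the repeat share among ill subjects, and uniform scaling of every subject's rate is not established: Protocol 1.2.2 reports Phase 2b reductions from 25.3% to 68.9% across subgroups that remain eligible. A reader might infer that the Type I error of H5 is inflated in general. It is not, as the no-effect and equal-repeat-share checks show.

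**The FAS population in estimand 5 might be read as contradicting the risk set.** SAP 9.4.4 states the risk set openly and the estimand's variable is CSRI symptoms, so this is a matter of wording.

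**Conclusion.** The covariate point holds without qualification: SAP 9.4.4 departs from Protocol 9.5 by one factor and does not declare it. The size of the effect cannot be derived.

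The longest-episode point holds in direction, on the condition that RTB101 lowers the repeat share among ill subjects. At the planned incidences with Poisson counts it is modest, with a two-sided excess of about 0.1 to 0.9 points. Anything larger, up to about 9% two-sided, needs the assumed overdispersion. H1 to H4 are unaffected. The documents do not support calling H5 invalid or requiring that the longest-episode rule be replaced.

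**What to change.** 1. SAP 9.4.4: add current-season influenza vaccination (Y/N) to the Cox covariates. The data are already collected, so this costs nothing.
2. SAP 9.4.4 and the index of tables: prespecify a first-CSRI analysis of H5 with the same model, reported beside the longest-episode result. State that the longest-episode hazard ratio reflects the number of CSRIs as well as their duration. The cost is one extra analysis of existing eDiary data. The first-CSRI analysis ignores later episodes and does not remove the selection of ill subjects after randomization.
3. SAP 9.2.2, estimand 5: word the population as FAS subjects with at least one CSRI, to match the risk set. This is a wording correction only.

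All three are SAP text. The protocol does not state the longest-episode rule and needs no amendment.
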